### **Completed by the Health Coach at Each Study Visit**

**Treatment Adherence:** Participant compliance with in-person health coaching visits will be measured as attendance; compliance with SMS messaging will be monitored by the health coach in real-time via a web portal. The study team will evaluate compliance with in-person visits and weekly SMS messaging by measuring attendance and % response rate to SMS prompts.

**Treatment Fidelity Monitoring:** In addition to audio recording each in-person health coaching visit and reviewing audio-recordings during weekly study team teleconferences with the PI's, Health Coaches will also be required to rate their performance and competence in delivering prescribed intervention content at each visit using an established Treatment Fidelity and Competence Rating Scale used by the PIs in previous NIH-funded lifestyle intervention trials.

**Response to Intervention Form:** The health coach will assess the participant's level of engagement, motivation and understanding of materials with five questions at the end of each monthly visit. This form has been used by our team in previous behavioral weight management studies.

**Body Mass Index (BMI):** BMI is correlated with direct measures of body fat like skinfold thickness measurements, bioelectrical impedance, densitometry (underwater weighing) and dual energy x-ray absorptiometry (DEXA), and is strongly correlated with various metabolic and disease outcomes, similar to more direct measures of body fatness. Because calculation requires only height and weight, it is inexpensive, easy to reproduce and relevant to public health guidelines. BMI will be assessed at each study visit using calibrated scales and stadiometers.

### **Completed by Participant and Community Support Worker at Study Midpoint and Endpoint**

**Feasibility, Appropriateness & Acceptability Questionnaire:** At every health coaching visit, both clients and case managers will be asked specifically to rank the feasibility of intervention implementation, appropriateness of the intervention and acceptability/usability of the intervention from their respective perspectives.

**Treatment/Program Satisfaction Questionnaire:** This satisfaction questionnaire has been used in NIH-funded weight loss studies, and has been modified for use in prior iOTA adaptations completed by our group. Clients and case managers will be asked to complete the satisfaction survey at 16 weeks and at the wrap-up visit; if a participant drops out prior to study completion, the team will ask for final satisfaction surveys of both case manager and client before study termination.

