### **AIM 3**

In this aim we will work with BJC BH and SFBHN to implement and evaluate the adapted iOTA-eSMI intervention that provides support for behavior change to increase physical activity and modify diet, in order to achieve clinically significant weight loss and/or prevent obesity, thereby reducing diabetes and cardiovascular disease risk in eSMI. For the proposed iOTA testing, all otherwise eligible eSMI clients who have experienced  $\geq 7\%$  increase in weight in the past 2 years and/or are currently overweight (BMI 25-29.9) or early class I obesity (BMI 30-32.49) by BMI will be offered participation in the adapted iOTA. Our proposed pilot study aims to assess feasibility, acceptability, tolerability, and target engagement and will explore one primary hypothesis: participants in the intervention group will show favorable change in body weight compared to clients in the Health Education Control group. Secondary analyses will assess iOTA effects BMI and on RDoC domains relevant to needed psychophysical skills and self-efficacy, exploring the relationship between weight change and target engagement. Feasibility, engagement and implementation challenges will be characterized, measured by i) enrollment & retention, ii) obesity intervention acceptability, iii) text response rates, iv) visit adherence v) client expectations, vi) fidelity and vii) CMHC staff-rated acceptability, appropriateness and burden. To achieve these goals, we will conduct a randomized controlled pilot study in 60 eSMI patients ages 18-45. Participants will be randomized 2:1 to 24 weeks in the Psych iOTA Program or in the Health Education Control program. Both intervention groups will have monthly in-person visits with a health coach. The iOTA group will receive daily text messages specific to health goals set during the in-person visits, and will receive treatment content that incorporates empirically supported approaches to increasing self-efficacy and psychophysical awareness. The Health Education Control group will receive education based on the Stanford health care self-management program developed by Kate Lorig and colleagues and modified to be similar to the iOTA intervention in number and length of visits. We will also obtain acceptability, appropriateness and feasibility feedback from case managers and clients on benefits, barriers, and suggested improvements to the SMS portion of the intervention during monthly in-person health coaching visits.

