#### **Randomization of participants:**

Participants will be randomized 2:1 to 24 weeks in the Psych iOTA Program or in the Health Education Control program. Both intervention groups will have monthly in-person, zoom, or telephone visits (lasting approximately 1 hour (Baseline and final visit lasting ~ 2 hours) with a health coach. Documentation of the screening and monthly visit assessments will be directly entered into a secure REDcap database by the Health Coaches at each site. Each site will have weight scales for documenting of weight changes.

The iOTA group will receive daily text messages specific to health goals set during the in-person visits, and will receive treatment content that incorporates empirically supported approaches to increasing self-efficacy and psychophysical awareness.

The Health Education Control group will receive education based on the Stanford health care self-management program developed by Kate Lorig and colleagues and modified to be similar to the iOTA intervention in number and length of visits. We will also obtain acceptability, appropriateness and feasibility feedback from case managers and clients on benefits, barriers, and suggested improvements to the SMS portion of the intervention during monthly sessions with PIs and staff at the Healthy Mind Lab located in the Taylor Avenue Building on the Washington University Medical Campus and at the South Florida Behavioral Health Network facilitates at our associated two Florida study sites (Fellowship House and Guidance Care Center) and at the Independence Center Organization in St. Louis, MO.

Participants unable to attend visits in person will have the option of attending study visits remotely by phone or by using a Washington University-approved video conferencing platform (Skype or Zoom) and digital links to study assessments in REDCap. For potential participants who have computer access and capability, study visits may be conducted via video conferencing. The health coach will use a secure, web-based, HIPAA-compliant, conferencing platform that employs encryption of video and audio content. Potential participants would receive an email or text message with a unique and secure link to join the video session by computer or mobile device.

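### Acceptability ratings are collected at the coaching visit and nothing keeps the answers from the coaches or PIs, so their absolute level is at risk of upward courtesy bias

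*Protocol*

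**What the plan says.** The Feasibility, Appropriateness & Acceptability Questionnaire stands in the Protocol under the heading "Completed by Participant and Community Support Worker at Study Midpoint and Endpoint". The text below that heading gives another timing: "At every health coaching visit, both clients and case managers will be asked specifically to rank the feasibility of intervention implementation". The Satisfaction Questionnaire, in the same section, is due at 16 weeks and at the wrap-up visit. Who administers it is not stated.

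On data entry, Protocol, *Randomization of participants*, says: "Documentation of the screening and monthly visit assessments will be directly entered into a secure REDcap database by the Health Coaches at each site". On delivery, the Aim 3 introduction says: "Both intervention groups will have monthly in-person visits with a health coach".

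Client and case manager feedback on the text-messaging component is described twice, with different settings. The Aim 3 introduction places the "suggested improvements to the SMS portion of the intervention during monthly in-person health coaching visits". *Randomization of participants* places the same feedback "during monthly sessions with PIs and staff at the Healthy Mind Lab" and at the other sites.

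The study is stated to be unblinded (Protocol, *Study Participants* under Aim 3). The SAP's analytic plan lists acceptability among the goals of the funding mechanism, and says that process variables within the active arm will be used to refine the intervention.

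**The concern.** A client asked to rate a programme while attending the session, with the person who has coached them for months involved in handling the data, has a reason to be polite. Neither document tells the client that the coach and the PIs will not see the answer. The same holds where feedback is given in a session with the PIs, who lead the study. In-person coaching sessions are also audio-recorded and reviewed by the PIs for fidelity, so anything said aloud in the visit can reach them too.

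The SAP puts formal testing of effects outside the scope of this pilot. What it must deliver is information on feasibility, acceptability, tolerability and target engagement. If ratings are lifted by courtesy, the team may carry into the planned larger trial a component that clients would have marked down in private.

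**Working it through.** The documents state no acceptability threshold, expected rate or precision, so there is no planned figure to reproduce. The check is a reading of the text, followed by an illustration of scale.

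**Reading the text**

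1. *When ratings are made.* At every coaching visit according to the text, at midpoint and endpoint according to the heading. Taking monthly as four-weekly (an assumption), 24 weeks give 24 / 4 = 6 visits after baseline. That is 6 × 60 = 360 scheduled client ratings on one reading and 2 × 60 = 120 on the other. The analysis data set therefore depends on which statement governs.
2. *Who fills in the form.* The heading names the participant and the community support worker. The digital battery that participants complete themselves at each visit does not list this questionnaire, so its mode of completion is not given.
3. *Who enters and sees the answers.* The rule that coaches enter monthly visit assessments is general. It carries no exception for ratings of the programme. Nothing in either document provides for confidentiality, a neutral administrator or restricted access to these responses.
4. *What the ratings are used for.* Within the iOTA arm they inform refinement of the intervention (SAP, analytic plan). They also enter exploratory analyses of how such variables relate to BMI and self-efficacy (SAP, exploratory analyses).

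**Scale, by illustration**

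Inputs from the documents: 60 participants randomized 2:1, so 60 × 2/3 = 40 in iOTA. Assumptions, not in the documents: a binary acceptable/not acceptable summary, a true rate of 70%, inflation of 0, 5 or 10 percentage points, and a reference mark of 32/40 = 80%.

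- Sampling precision, 1.96 × √(p(1−p)/40): at p = 0.70, 1.96 × √(0.21/40) = 0.142, or 14.2 points. At p = 0.80, 1.96 × √(0.16/40) = 0.124, or 12.4 points.
- Exact binomial probability that at least 32 of 40 rate the programme acceptable:

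| Inflation | Observed-rate parameter | P(X ≥ 32 of 40) |
|---|---|---|
| none | 0.70 | 0.11 |
| 5 points | 0.75 | 0.30 |
| 10 points | 0.80 | 0.59 |

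Under these assumptions, 10 points of inflation turn a result with about a one-in-nine chance into one that is more likely than not. The shift is smaller than the 95% half-width, so the ratings alone would not reveal it.

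**The case against.** The best reply is that the documents do not show the bias. The heading makes the questionnaire self-completed, and a phrase about the coaching visit fixes the time, not the recipient. A reader might infer that clients give their ratings aloud to the coach, but no sentence says so. The two statements about monthly feedback concern the text-messaging component and may describe formative discussion, not this questionnaire. One of them names staff as well as PIs, so the listener need not have built or delivered the programme. All this stands, and it is why the point is put as a risk. It does not answer the general rule on coach entry or the absence of any confidentiality.

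A second reply is that coaches see both arms, so a common courtesy effect would largely cancel in a comparison. That is fair for the difference between arms. It gives no protection to the level within iOTA, which is what the SAP uses.

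Third, acceptability is exploratory, has no go/no-go threshold, and is read alongside retention, visit adherence and text response rates, which are not courtesy ratings. Case managers also rate, and they have less reason to please a coach. These facts limit the consequence. They do not replace a candid client rating.

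Finally, because the unblinded coach also measures BMI and enters visit data, a reader might infer that the primary weight outcome is biased towards iOTA. The documents do not support that: "BMI will be assessed at each study visit using calibrated scales and stadiometers", in both arms, and nothing indicates differential reading. Photographing the scale display would not help, since it would be done by the same unblinded coach and would check transcription only.

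**Conclusion.** The concern holds as a risk to the absolute level of client-rated feasibility, appropriateness and acceptability. It rests on three textual facts: ratings fall at the coaching visit, the coaches who deliver the programme enter visit assessments, and no safeguard keeps the answers from coaches or PIs. It also rests on the ordinary expectation that people rate more kindly when the provider may see the answer.

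The likely direction is upward. The size is unknown, and the probabilities above depend entirely on assumed values. The risk is clearest for clients and weaker for case managers. It does not amount to a finding that acceptability is biased, and it does not extend to weight.

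This should be changed before ratings are collected, because the remedy is cheap and the measure is one of the pilot's stated goals. The conflicts over timing and setting are plain on the page and need correcting in any case.

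**What to change.** 1. Have clients and case managers complete the Feasibility/Appropriateness/Acceptability and Satisfaction forms themselves through a REDCap survey link, on a site tablet or their own phone, at the end of the visit with the coach out of the room. If the form is not done then, or the visit is remote, send the link afterwards with automated reminders.
2. In *Randomization of participants*, exempt these two forms from entry by health coaches.
3. Set REDCap user rights so that coaches and PIs cannot see identifiable responses until data collection ends, and tell respondents this on the form.
4. State one timing for the acceptability questionnaire, so that heading and text agree, and one setting for feedback on the text messages, so that the Aim 3 introduction and *Randomization of participants* agree. Say whether that feedback is separate from the questionnaire.
5. Report the response rate with the ratings.

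The cost is survey set-up, user rights and edits to three protocol sections. The trial already uses REDCap links for remote assessments and a participant-completed digital battery, and being able to use a mobile device is necessary for participation, so no new system is needed. The downside is that some responses may be lost. If disengaged clients are the ones lost, that too could raise the observed level, which is why completion at the visit comes first and the later link is the fallback.

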### **Participant Compensation:**

Participants will be compensated with a gift-card in the amount of \$25 for every completed study visit.

### **Participant Withdrawal:**

- Participants may withdraw at any point during or after the completion of the study with no penalty by contacting the study team.
- Investigators may choose to withdraw a participant from the study if it is unsafe to continue participation.
- If a subject withdraws from the study, the research team may only use and share information already collected for the study. Subject information may still be used and shared as necessary to maintain the integrity of the research, for example, to account for a participant's withdrawal from the research study or for safety reasons.

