## **Definitions of Adverse Events**

The most serious risk in the proposed research is any adverse outcome that may jeopardize the welfare of participants or caregivers. Possible adverse events that are anticipated include an unintentional disclosure of personal health information to an unauthorized individual. Additionally, it is possible that during the tele-health mediated assessment phase of this project, the individual or their caregiver could conceivably experience an acute medical event requiring immediate medical attention. In the unlikely event that this were to occur, the study staff would assist the participant or their caregiver in alerting local EMS, or alternatively would contact local EMS on their behalf.

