## **Expectedness**

- AEs that are unanticipated will be reported immediately to the Washington University in St. Louis IRB by the PI. The IRB will determine whether it is appropriate to stop the study protocol temporarily or will provide suggestions/modifications to the study procedures. Possible modifications include adding these possible adverse events to the consent form and re-consenting all study participants. The PI will be responsible for monitoring participant safety on a monthly basis at regularly scheduled research meetings. The PI will keep a written log of all adverse events and ensure that the IRB is contacted immediately. The PI will also keep a log of the outcome of IRB decisions regarding adverse events and enforce any changes that need to occur as a result of the IRB decisions. If the preliminary outcome data indicates harmful impact of the program to caregivers or their families, the Washington University in St. Louis committee will be notified and it is possible that the study will be discontinued.

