## **Data Collection Procedures for Adverse Events**

- The PI will be responsible for monitoring participant safety on a monthly basis at regularly scheduled research meetings. The PI will keep a written log of all adverse events and ensure that the IRB is contacted immediately and will also keep a log of the outcome of IRB decisions regarding adverse events and enforce any changes that need to occur as a result of the IRB decisions. If the preliminary outcome data indicates harmful impact of the program to caregivers or their families, the Washington University in St. Louis committee will be notified and it is possible that the study will be discontinued.

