## **Post-study Adverse Event**

There are no anticipated post-study adverse events that would accrue from cross-referencing or analysis of research data since this information will not be returned to the family.

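### The only stated decision for a participant who is unsafe to continue is withdrawal from the study; stopping the intervention is not separated from stopping weights and adverse event follow-up

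*Protocol*

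**What the plan says.** The Participant Withdrawal section of the protocol lets participants leave at any time and then states the investigator's option: "Investigators may choose to withdraw a participant from the study if it is unsafe to continue participation". The next rule limits data after withdrawal: "If a subject withdraws from the study, the research team may only use and share information already collected for the study". An exception follows: "Subject information may still be used and shared as necessary to maintain the integrity of the research", with accounting for a withdrawal and safety given as examples.

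The one planned exit contact is under the satisfaction questionnaire: "if a participant drops out prior to study completion, the team will ask for final satisfaction surveys of both case manager and client". No weight, reason for leaving or event status is requested there.

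Study weights are taken at study visits, on calibrated scales, at up to 10 visits over 9 months (Body Mass Index entry; Data Analysis/ Statistical Considerations). The iOTA arm is also prompted by text each week to report weight, and the text data are stored and sent to the research team (iOTA intervention; Data Management Procedures and Confidentiality).

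The safety sections give other actions. In an acute event, "the study staff would assist the participant or their caregiver in alerting local EMS". At study level, "The IRB will determine whether it is appropriate to stop the study protocol temporarily", and discontinuation of the study is possible. On recording, "The PI will keep a written log of all adverse events and ensure that the IRB is contacted immediately". Monitoring by the PI, 24-hour reporting to the IRB, and reports to the NIH program officer are also specified.

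**The concern.** Two decisions are merged. One is whether a person should go on receiving coaching and texts. The other is whether the study should go on measuring that person and following an event. A safety problem often calls for stopping the first and seldom for stopping the second. With only withdrawal from the study on offer, a coach or investigator who follows the text has no planned way to do one without the other.

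This matters most for tolerability, which both the rationale for study length and the SAP's analytic plan name as an aim of the pilot. People removed for safety are those whose event outcomes say most about it. Weight change is the primary outcome, and those removed may differ in weight course from those who stay, so their missing weights may be informative.

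**Working it through.** **Reading the text.** I looked for any provision that stops the intervention for one person while follow-up continues.

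- The call to emergency services responds to an acute event. It is not a decision on participation.
- The IRB's pause or modification, and discontinuation, act on the study.
- The 12 weeks of texts alone are scheduled for both groups, so they are not a step-down for an individual.
- The integrity and safety exception allows information to be used and shared. It schedules no collection.
- The exit contact is for those who drop out. Whether that includes people removed by an investigator is not stated.
- The adverse event sections require a log and reports. The outcome they name for logging is that of IRB decisions; no contact with a removed participant is planned to learn how the event ended.
- The post-study section says "There are no anticipated post-study adverse events that would accrue from cross-referencing or analysis of research data", which concerns data analysis and not an event still open at removal.

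**Counts from the plan's numbers.** 60 randomised 2:1 gives 60 x 2/3 = 40 and 60 x 1/3 = 20. One person with an unknown event outcome is 1/40 = 2.5% of the iOTA arm or 1/20 = 5% of control. Removal after visit k loses at most 10 - k study weights: 9, 6 or 3 for k = 1, 4 or 7. These are upper bounds, because the plan says up to 10 visits.

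**Effect on the weight comparison.** The documents give no removal rate or standard deviation, so this is an illustration on assumed inputs: a linear mixed model with arm, month and arm x month; random intercept SD 15 kg, slope SD 0.5 kg/month, residual SD 1 kg; ten visits at months 0 to 9; removal after visit 4 (month 3). The removed person's weight then drifts linearly above prediction, to d kg at month 9. The estimate is 9 x the arm-by-month slope, i.e. the arm difference (iOTA minus control) in change from baseline to month 9.

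*Standard error, complete data.* The sum of (t - 4.5)² over t = 0 to 9 is 82.5. The variance of one person's slope is 0.5² + 1²/82.5 = 0.2621. SE = 9 x sqrt(0.2621 x (1/40 + 1/20)) = 9 x sqrt(0.01966) = 1.262 kg.

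*Shift from one removal, d = 3.* The drift at months 4 to 9 is 0.5, 1, 1.5, 2, 2.5, 3. Its contribution to that person's slope is the sum of (t - 4.5) x drift, divided by 82.5: 29.75/82.5 = 0.3606 kg/month, or 9 x 0.3606 = 3.245 kg over nine months. Losing it moves the arm mean by 3.245/40 = 0.081 kg in iOTA or 3.245/20 = 0.162 kg in control.

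An exact generalised least squares fit of the same model gives these shifts against complete follow-up:

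| Removed (iOTA, control) | d = 1 kg | d = 3 kg | d = 5 kg |
|---|---|---|---|
| 1, 0 | -0.027 | -0.081 | -0.135 |
| 0, 1 | +0.054 | +0.162 | +0.271 |
| 4, 1 | -0.054 | -0.162 | -0.271 |
| 2, 2 | +0.054 | +0.162 | +0.271 |
| 4, 2 | 0 | 0 | 0 |

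For d = 3 and one removal, 0.081/1.262 = 0.06 SE and 0.162/1.262 = 0.13 SE. The SE rises to 1.264 (one iOTA removal) or 1.271 kg (one control removal). For the difference in weight level at month 9, rather than in change, the SE is 4.29 kg and the d = 3 shifts are -0.067 and +0.134 kg. The effect is small on either scale.

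**The case against.** The strongest case against the point is that nothing here is forbidden. The withdrawal rule is permissive and speaks of participation being unsafe, not of coaching or texts being unsafe. The limit to data already collected is worded for a subject who withdraws, so it can be read as leaving out people whom an investigator removes. That reading is reasonable, but the protocol does not state it. A reader might infer that the protocol bars follow-up after a safety removal; the text does not support that.

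A reader might also infer that event outcomes go unrecorded. That is too strong. There is a log of all adverse events, regular monitoring and prompt reporting. Participants receive case management at the study centres, so a clinical channel exists outside study visits. What stands is narrower: no contact after removal is planned to follow an open event.

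Nor is it right that all weights depend on visits. The iOTA arm has weekly self-reported weights by text. They are not the calibrated measurements, control has no such prompt described, and they would end if the texts were stopped.

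Finally, the consequence is slight. No removal rate is given, it could be zero, and the SAP places effect-size estimation outside its scope. All of that stands, and it is why this is a minor point.

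**Conclusion.** The point holds as a minor one and the change is a cheap improvement. The only stated individual-level safety decision is withdrawal from the study, and follow-up after removal is not planned. The loss is mainly tolerability and event information: 2.5 or 5 percentage points of an arm for each person whose event outcome is unknown, and up to 9, 6 or 3 study weights.

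A reader might infer that the primary weight comparison is materially biased. The documents do not support that. On the assumed inputs one removal moves it by 0.06 or 0.13 SE; the direction depends on which arm loses more people, and equal removal rates give no shift. The SDs, the timing and the 1 to 5 kg drift are assumptions, and no stated decision rests on the estimate. The consent form is not in the documents available and may say more.

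**What to change.** 1. Reword the Participant Withdrawal section so that an investigator's safety decision stops the intervention (coaching, texts or both). Scheduled weights and adverse event follow-up continue, remotely if needed as the protocol already allows for visits, and without coaching content, unless the participant declines or the assessment is itself unsafe. State that the limit to data already collected applies to participants who withdraw consent. The criteria for stopping stay with the investigators.
2. Extend the existing exit contact, for people who drop out and people who are removed, to ask for a final weight (flagged as measured or self-reported), the reason for leaving and the status of any open adverse event.

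Cost: protocol wording, a check that the consent form agrees, and a short weight-only contact for removed participants, since weights are now taken at coaching visits. One exit contact is $25 if paid as a visit, plus an assumed 15 to 30 minutes of coach time. Full follow-up after removal at visit 4 is at most 6 x $25 = $150, and 6 x 0.25 to 0.5 h = 1.5 to 3 coach hours, or 6 hours if each contact took the full one-hour visit. Some contacts will be declined, and some weights will be self-reported and must be flagged so that measurement modes are not mixed unnoticed in the primary outcome.
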